8. APPENDIX 3: PATIENT DIARY DATA AND SYMPTOM RECORD FOR ADULTS AND CHILDREN

The purpose of the patient diary is for all adults (13 years and older) to record any symptoms of influenza-like illness for the duration of the study. Temperature and date and time of drug administration should also be recorded on the patient diary.

Date of assessments
dd mm yy

Time of assessments
(24 hr clock) h min

Vital signs

Temperature °C

Symptoms of influenza-like illness

Please record the worst you have felt since the last assessment.
 Please mark one box only per symptom.
 The information you provide is very important and will remain strictly confidential.

	absent 0	mild 1	moderate 2	severe 3
1. Nasal congestion				
2. Sore throat				
3. Cough				
4. Aches and pains				
5. Fatigue (tiredness)				
6. Headache				
7. Chills/sweats (feverish)				

Please inform study staff at your next visit of any medications that you have taken today or any medical problems that you have experienced.

Patient Diary Data and Symptom Record for Children

Temperature and date and time of drug administration will also be recorded on the patient diary.

Study medication administration (if applicable)

Date of dose	Time of dose (24 hr clock)	Bottle A amount mg	Bottle B amount mg
 <small>dd mm yy</small>	 :  <small>h min</small>		
Date of assessments	Time of assessments (24 hr clock)		
 <small>dd mm yy</small>	 :  <small>h min</small>		

Vital signs

Temperature . °C

Symptoms of influenza-like illness

Please record the worst you have felt since the last assessment.
Please mark one box only per symptom.
The information you provide is very important and will remain strictly confidential.

	No Problem 0	Minor Problem 1	Moderate Problem 2	Major Problem 3	Don't Know or not Applicable 4
1. Poor appetite					
2. Not sleeping well					
3. Irritable, cranky, fussy					
4. Feels unwell					
5. Low energy, tired					
6. Not playing well					
7. Crying more than usual					
8. Needing extra care					
9. Clinginess					
10. Headache					
11. Sore throat					
12. Muscle aches or pains					
13. Fever					
14. Cough					
15. Nasal congestion, runny nose					
16. Vomiting					
17. Not interested in what's going on					
18. Unable to get out of bed					

This form was filled out by:

- 1 Parent
- 2 Other relative
- 3 Nanny
- 4 Subject
- 5 Other *specify*

Please inform study staff at your/your child's next visit of any medications that you/your child have taken today or any medical problems that you/your child have experienced.

9. APPENDIX 4: HISTORICAL CONTROL SPECIFICATION FOR EFFICACY

Table A4.1. Studies from which historical controls (both placebo and treated) may be selected from.

*Tables and plots from Statistical Programmer Analysts (SPA)

#	Label	Protocols to include	Specifications	Comments
1	1:1 Otherwise Healthy Placebo Adults ITTi	WV15670, WV15671	Match each NV20234 adult mITTi patient with 1 ITTi placebo-treated patient who have same age and gender	Potential additional studies: M76001, WV15730, WV15758
2	1:>1 Otherwise Healthy Placebo Adults ITTi	WV15670, WV15671	Match each NV20234 adult mITTi patient with ITTi placebo-treated patients who have same age and gender.	Potential additional studies: M76001, WV15730, WV15758
3	1:1 At risk Placebo Adults ITTi	WV15812, WV15872	Match each NV20234 adult mITTi patient with ITTi placebo-treated patient who have same age and gender.	Potential additional studies: WV15819, WV15876, WV15978 and WV15707
4	1:>1 At risk Placebo Adults ITTi	WV15812, WV15872	Match each NV20234 adult mITTi patient with ITTi placebo-treated patient who have same age and gender.	Potential additional studies: WV15819, WV15876, WV15978 and WV15707
5	ITTi treated adult datasets		Repeat datasets 1-2 matching NV20234 patients with historical treated patients by randomised treatment.	

N.B. NV20234 will focus on the mITTi population. In historical studies, the definition of ITTi population was identical to the current mITTi population. Historical studies contain a standard population with a more strict definition i.e. “randomised, infected, no major violations and who received at least the first six scheduled doses of treatment within 72 hours or who received the first five doses within 72 hours but then went on to take nine out of ten doses”, however this population is not present in the current study. Adolescents will only be listed for efficacy.

Variables required for each dataset:

Variables required in each of the datasets, where available: NV20234 patient ID, centre ID number, country, age, gender, vaccination status, primary flu type, primary flu A subtype, randomised treatment, time from onset of symptoms to start of drug, time to alleviation of all symptoms, time to alleviation of individual symptoms, time to cessation of viral shedding, AUC viral titer, peak viral titer, AUC total symptom score, AUC individual symptom score, time to alleviation of fever.

10. APPENDIX 5: SUMMARY OF MAIN EFFICACY ANALYSES

Table A5.1. List of main efficacy analyses

*Tables and plots from Statistical Programmer Analysts (SPA). Suffixes: AD = adults (age ≥ 18), ADOL = adolescents (13 ≤ age < 18), CH = children (1 ≤ age < 18), PED = paediatric (1 ≤ age <13).

**Benchmarking plots contain median TTR and 90% CI for standard dose, double dose, combined dose, historical control and historical treated (separate plots will contain 95% CI)

N.B. Median differences will be obtained using the Hodges-Lehmann estimator and associated Moses CI. TTR of symptoms and temperature will be assessed in adults (≥18), in adults and adolescents (≥13), and paediatrics (<13) separately; for all other efficacy, virology and safety data adults will be separated from children (<18).

Endpoint	Analysis	Comparisons	Population	Purpose	Age groups	SPA output*
TTR all symptoms	Kaplan-Meier median and 95%CI	Conventional- double	mITTi , ITTi, ITT	Main dose-response comparison	Adults Adults + Adolescents Paediatric	t_ef_ttr_ALLEVA S_MITi_AD_95 g_km_ttr_LLEVA S_MITi_AD_95 t_ef_ttr_ALLEVA S_ITi_AD_95 g_km_ttr_LLEVA S_ITi_AD_95 t_ef_ttr_ALLEVA S_IT_AD_95 g_km_ttr_ALLEVA AS_IT_AD_95

TTR all symptoms	Kaplan-Meier median and 90%CI	a. conventional b. double c. combined d. historical placebo e. historical treated	mITTi	Main comparison with historical control: NV20234 treatment against Historical Otherwise Healthy 1:1	Adults	t_ttr_hc_5g_1to1_ALLEVAS_MITI_AD_90 g_km_ttr_5g_1to1_ALLEVAS_MITI_AD_90
TTR all symptoms	Kaplan-Meier	a. conventional b. double c. combined d. historical placebo e. historical treated	mITTi	NV20234 treatment against Historical Otherwise Healthy 1:>1	Adults	t_ttr_hc_5g_1tom_ALLEVAS_MITI_AD_90 g_km_ttr_5g_1tom_ALLEVAS_MITI_AD_90
TTR all symptoms	Kaplan-Meier	a. conventional b. double c. combined d. historical placebo e. historical treated	mITTi	NV20234 treatment against at risk 1:>1	Adults	t_ttr_hc_5g_atrisk_ALLEVAS_MITI_AD_90 g_km_ttr_5g_atrisk_ALLEVAS_MITI_AD_90
TTR all symptoms	Kaplan-Meier	a. conventional b. double c. combined d. historical placebo e. historical treated	mITTi	NV20234 – Historical control Otherwise Healthy 1:1 Sensitivity for follow-up observational period : only including symptom scores recorded ≤25 days	Adults	t_ttr_hc_5g_25d_ALLEVAS_MITI_AD_90 g_km_ttr_5g_25d_ALLEVAS_MITI_AD_90
TTR all symptoms	Kaplan-Meier	a. conventional b. double c. combined d. historical placebo e. historical treated	mITTi	NV20234 – Historical Otherwise Healthy 1:1 Sensitivity analysis: patients who were dosed no more than 48 hours after symptom onset	Adults	t_ttr_hc_5g_48h_ALLEVAS_MITI_AD_90 g_km_ttr_5g_48h_ALLEVAS_MITI_AD_90
TTR all symptoms	Kaplan-Meier	a. conventional b. double	mITTi	Subgroup analysis 
 • By vaccination status (yes/no) • By transplant status (yes/no) • By ≤ 48, >48 h from symptoms onset • By geographical region 	Adults	t_ef_ttaas_vac_MITI_AD t_ef_ttaas_trans_MITI_AD t_ef_ttaas_onset_MITI_AD t_ef_ttaas_reg_MITI_AD

TTR individual symptoms	Kaplan-Meier	Treatment Responses by treatment arms	mITTi	Main Summary for this endpoint	Adults Children	t_ef_ttais_MITI_AD t_ef_ttais_MITI_CH
Time to cessation viral shedding	Kaplan-Meier	Treatment Responses by treatment arms	mITTi	Dose-Response main analysis for this endpoint	Adults Children	t_ef_ttr_CESCLT_MITI_AD t_ef_ttr_CESPCR_MITI_AD g_km_ttr_CESCLT_MITI_AD g_km_ttr_CESPCR_MITI_AD t_ef_ttr_CESCLT_MITI_CH t_ef_ttr_CESPCR_MITI_CH g_km_ttr_CESCLT_MITI_CH g_km_ttr_CESPCR_MITI_CH
Time to cessation viral shedding	Kaplan-Meier	Treatment median [90% CI] Responses for : NV20234 conventional, NV20234 double, NV20234 pooled, historical treatment conventional, historical treatment double, historical placebo for conventional, historical placebo for double, historical placebo for pooled.	mITTi	Benchmarking plot	Adults All CI's on one plot but also split by a) pooled b) conventional c) double	g_km_t1_t2_hist_plac_treat_TTCVS_MITI_AD_95 g_km_t1&2_hist_plac_treat_TTCVS_MITI_AD_95 Repeated 1:1 and 1:>1 matches
TTR fever	Kaplan-Meier	Treatment Responses by treatment arms	ITT, ITTi ,mITTi	Dose-Response main analysis for this endpoint	1) Adults 2) Adults+Adolescents 3) Paediatric	g_ef_ttr_RESF_ITT_AD g_ef_ttr_RESF_ITT_PE

						g_ef_ttr_RESF_I TT_AD_ADOL
						t_ef_ttr_RESFBL _ITT_AD
						t_ef_ttr_RESFBL _ITT_PE
						t_ef_ttr_RESFBL _ITT_AD_ADOL
						g_ef_ttr_RESF_I TI_AD
						g_ef_ttr_RESF_I TI_PE
						g_ef_ttr_RESF_I TI_AD_ADOL
						t_ef_ttr_RESFBL _ITI_AD
						t_ef_ttr_RESFBL _ITI_PE
						t_ef_ttr_RESFBL _ITI_AD_ADOL
						g_ef_ttr_RESF_ MITI_AD
						g_ef_ttr_RESF_ MITI_PE
						g_ef_ttr_RESF_ MITI_AD_ADOL
						t_ef_ttr_RESFBL _MITI_AD
						t_ef_ttr_RESFBL _MITI_PE

						t_ef_ttr_RESFBL_MITI_AD_ADO L
TTR fever	Kaplan-Meier	Treatment median [90% CI] Responses for : NV20234 conventional, NV20234 double, NV20234 pooled, historical treatment conventional, historical treatment double, historical placebo for conventional, historical placebo for double, historical placebo for pooled.	mITTi	Benchmarking plot**	1) Overall 2) Age cohort (>= 18 Y, < 18 Y) All CI's on one plot but also split by a) pooled b) conventional c) double	g_km_t1_t2_hist plac_treat_RES F_MITI_AD_90 g_km_t1&2_hist plac_treat_RES F_MITI_AD_90 Repeated 1:1 and 1:>1 matches
AUC total symptom scores	Median, IQR	Treatment Responses by treatment arms	mITTi, ITT, ITTi	Dose-Response main summary for this endpoint	Adults only	g_auc_ALLEVA S_AD t_auc_ALLEVAS AD
AUC total symptom scores	Median, IQR	Treatment median [IQR] for: NV20234 conventional, NV20234 double, NV20234 pooled, historical treatment conventional, historical treatment double, historical placebo for conventional, historical placebo for double, historical placebo for pooled.	mITTi	Benchmarking plot	For adults only : All plots on one plot but also split by a) pooled b) conventional dose c) double dose	g_km_t1_t2_hist plac_treat_AUC ALLEVAS_MITI_ AD_90 g_km_t1&2_hist plac_treat_ALLE VAS_MITI_AD_ 90 Repeated 1:1 and 1:>1 matches
AUC individual symptom score	Median, IQR	Treatment Responses by treatment arm	mITTi	Dose-Response main summary for this endpoint	Adults	g_auc_ALLEVIS _AD t_auc_ALLEVIS _AD
AUC viral titer	Median, IQR	Treatment Responses by treatment arm	mITTi	Dose-Response main summary for this endpoint	Adults Children	g_ef_auc_AUCC LT_MITI_AD t_ef_auc_AUCC LT_MITI_AD

						t_ef_auc_AUCC LT_MITI_CH t_ef_auc_AUCP CR_MITI_CH t_ef_auc_AUCP CR_MITI_CH
AUC viral titer	Plot Median, IQR	Treatment median [IQR] Responses for: NV20234 conventional, NV20234 double, NV20234 pooled, historical treatment conventional, historical treatment double, historical placebo for conventional, historical placebo for double, historical placebo for pooled.	mITTi	Benchmarking plot	All plots on one plot but also split by a) pooled b) conventional c) double	g_km_t1_t2_hist plac_treat_AUC CLT_MITI_AD_90 g_km_t1&2_hist plac_treat_AUCCLT _MITI_AD_90 Repeated 1:1 and 1:>1 matches
Peak viral titer	Median, IQR	Treatment Responses by treatment arms	mITTi, ITT, ITTi	Dose-Response main summary for this endpoint	a) Adults b) Children	t_ef_auc_PEAK CLT_MITI_AD t_ef_auc_PEAK CLT_MITI_PE t_ef_auc_PEAK PCR_MITI_AD t_ef_auc_PEAK PCR_MITI_PE
Virus shedding	Proportions	Percentage of patients with viral shedding by baseline and planned visit.	mITTi	Main summary table	a) Adults b) children	t_ef_shed_CLTR _MITI_AD t_ef_shed_CLTR _MITI_CH t_ef_shed_PCR _MITI_AD t_ef_shed_PCR MITI_CH

Viral Load RT-PCR	Change from baseline in viral load RT-PCR	Summary Statistics (Mean, SD, Median, Range)	mITTi	Main summary table	Adults Children	t_ef_cfb_PCR_MITI_AD t_ef_cfb_PCR_MITI_CH
Viral Load Culture	Change from baseline in viral load from culture	Summary Statistics (Mean, SD, Median, Range)	mITTi	Main summary table	Adults Children	t_ef_cfb_CLTR_MITI_AD t_ef_cfb_CLTR_MITI_CH
Secondary Illnesses (SI)	summary only	N(%) by treatment group	Safety	Main summary table	1) Overall 2) Adult 3) Children Split by : a) any SI starting at any time b) any SI starting at any time that is treated with ant biotics c) SI started >=48 hours after start of study treatment that is treated with ant biotics	t_ae_secil_MITI t_ae_secil_ANTI B_SE

11. **APPENDIX 6: VIRAL MUTATIONS ASSOCIATED WITH RESISTANCE**

Table A6.1. USPI table with Neuraminidase (NA) Amino Acid Substitutions Associated with Reduced Susceptibility to Oseltamivir*

Influenza A N1 (N1 numbering in brackets)	
I117V (I117V)	E119V (E119V)
R152K (R152K)	Y155H (Y155H)
F173V (F174V)	D198G/N (D199G/N)
I222K/R/T/V (I223K/R/T/V)	S246N (S247N)
G248R+I266V (G249R+I267V)	H274Y (H275Y)
N294S (N295S)	Q312R+I427T (Q313R+I427T)
N325K (N325K)	R371K (R368K)
Influenza A N2	
E41G	
E119I/V	D151V
I222L/V	Q226H
SASG245-248	S247P
R292K	N294S
Influenza B (B numbering in brackets)	
E119A (E117A)	
P141S (P139S)	G142R (G140R)
R152K (R150K)	D198E/N/Y (D197E/N/Y)
I222L/T/V (I221L/T/V)	A246D/S/T (A245D/S/T)
H274Y (H273Y)	N294S (N294S)
R371K (R374K)	G402S (G407S)

*All numbering is N2, except where indicated

Haemagglutinin (HA) Amino Acid Substitutions Associated with Reduced Susceptibility to Oseltamivir

According to the current Tamiflu label, HA mutations should include A28T and R124M in influenza A H3N2 and H154Q in H1N9.

Per 2016 FDA feedback: *'the previously-listed substitutions A28T and R124M are now referred to as A11T and R453M, respectively, consistent with the convention of numbering from the beginning of the processed HA (without the signal peptide). We removed previously listed substitutions that were identified in strains not currently relevant to humans (H154Q in H1N9).'*" In summary, per FDA communication the HA residues to be included on the resistance list (renamed nomenclature, taking into account only the mature protein, w/o the signal peptide) are A11T, K173G, and R453M in H3N2; and H99Q in influenza B virus (no HA mutations listed for H1N1)

12. **APPENDIX 7: ALGORITHMS USED FOR DERIVATION AND SUMMARIES OF TIME TO ALLEVIATION OF ALL SYMPTOMS**

[figure not shown]
The purpose of this document is to describe the algorithm used to derive and analyse the Time To Resolution of all symptoms in the Tamiflu program (adults + adolescents).

Time to alleviation (TTA) of all symptoms (Efficacy VAD variable TALLSYMP), was calculated as the time **from start of study drug (Time=0) to the start of the first 24 hour period in which** all 7 symptoms were less than or equal to 1 and they remained at one or less for at least 21.5 hours, i.e., up to the end of the 21.5 hour period.

Example of Calculation of the Primary Efficacy Parameter: Time to Alleviation of all Symptoms

Pharmaceuticals

For subjects with missing data or who withdrew or ceased recording data prior to alleviation, data was imputed according to the following rules:

At the individual symptom level, a missing value was estimated by linear interpolation between the previously available assessment and the subsequently available assessment.

If the interpolated value was ≤ 1 for the first time (e.g. interpolation between a score of 2 and 0 gave 1) then the interpolated time point was not considered as the beginning of the 24 hour period that determined whether alleviation of that symptom had occurred, instead, the beginning of the 24 hour period started at the next observed time point at which the value was ≤ 1 . The VAD variables which denote missing data rules are TESTTYPE AND DATETYPE (refer to the efficacy VAD specifications for details).

If symptoms were missing, 0 or 1 at baseline and were subsequently recorded as missing, 0 or 1 for at least 21.5 hours, then the TTA of all symptoms was set to

missing. [Corresponding Efficacy VAD variables TALLSYMP=. And CENSORED=0.]

If all non-missing baselines symptoms were > 1 at baseline and recovered (<=1) immediately and remained <=1 for at least 21.5 hours OR if all non-missing baselines symptoms were > 1 at baseline and no further recordings of symptom scores had been recorded, then the Time to Alleviation of All symptoms was 0.

[Corresponding Efficacy VAD variables TALLSYMP=0 and CENSORED=0]

For Paediatric studies, should a subject only have No/mild symptoms from baseline onwards, and subsequent visits satisfy the 21.5 hour rule, then set TALLSYMP=0 and CENSORED=0.

Subjects withdrawing prior to alleviation of symptoms were **censored** at the time of withdrawal. [denoted in the efficacy VAD as CENSORED=1]

The primary endpoint was compared between groups using statistical methodology appropriate for survival data since censored data is present. The within-treatment group summary measures of median duration, was estimated from the Kaplan-Meier curve. A weighted Mantel-Haenszel test was used to formally test for a between-treatment group effect since the proportional hazards assumption was considered unlikely to hold *a priori*.

The weighting scheme used was the generalised Gehan Wilcoxon weights in which the weighting is equal to the number in the risk set.

Kaplan-Meier graphs of duration of symptoms according to treatment group were provided. Estimates of the difference between median durations were provided by subtracting the observed treatment group medians obtained from the Kaplan-Meier curve and estimating between group variability through bootstrapping. The dataset was sampled 2000 times in order to provide 95% confidence intervals using the percentile method (Efron 1993).

The bootstrap methodology had previously been applied within the influenza clinical trial field by the MIST group (MIST 1998) when comparing time to alleviation of illness in subjects treated with inhaled Zanamivir or placebo.

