4.4 EFFICACY ANALYSIS

All efficacy endpoints are considered secondary or exploratory. As no formal efficacy hypothesis is being tested, treatment differences presented in any efficacy analyses will be reported with associated confidence intervals (CIs) only. Efficacy endpoints will be summarized by age group. All summaries and analyses are described below and listed in [Appendix 5](#). All efficacy analyses will be based on the mITTi and ITTi populations. ITT will be presented for the main efficacy TTR summary tables (all symptoms and temperature only) to investigate the effect of treatment in a “real world” scenario, i.e. unknown infection status and/or adherence. N.B. Regulatory bodies have asked for these outputs in pivotal studies.

All efficacy summaries and analyses will be carried out separately for adults (patients ≥ 18 years) and paediatrics (patients <13 years old). Adolescent data (patients aged between ≥ 13 and <18 years old) will be listed as appropriate.

As the symptom data are recorded on patient diaries, data errors cannot be queried. Obvious data errors, i.e. temperature 100°C , will be excluded and documented. For duplicated data, the worst evaluation will be used to obtain conservative estimates.

The endpoints as described in the protocol have been expanded to give sufficient information of the derivations required, e.g. *symptom scores* was the endpoint defined in the protocol but *Time To Resolution of symptom scores* is how it is described in the SAP.

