4.8 VIROLOGY

The main virology outputs are:

- Incidence of persistent shedding (%), defined as $< 1 \log_{10}$ viral load (vp/mL) reduction at end of treatment compared with baseline.
- Summary of IC_{50} at baseline and fold-change over time by treatment group split by flu type and subtype using descriptive statistics: mean, SD, median, IQR, range.

- Summary of viral load in \log_{10} vp/mL for patients with resistant phenotype or genotype at baseline (ITT).
- Summary of viral load change from baseline over time in \log_{10} TCID₅₀ (viral culture) (adults mITTi).
- Summary of viral load change from baseline over time in \log_{10} TCID₅₀ (viral culture) (paediatrics mITTi).
- Summary of viral load change from baseline over time in \log_{10} vp/mL (RT-PCR) (adults mITTi).
- Summary of viral load change from baseline over time in \log_{10} vp/mL (RT-PCR) (paediatrics mITTi).
- Incidence of patients with viral shedding in \log_{10} TCID₅₀/mL and in \log_{10} vp/mL by visit (adults and adolescents mITTi)
- Incidence of patients with viral shedding in \log_{10} TCID₅₀/mL and in \log_{10} vp/mL by visit (paediatrics mITTi).

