6. APPENDIX 1: PROTOCOL SYNOPSIS

TITLE: A DOUBLE BLIND, RANDOMIZED, STRATIFIED, MULTI-CENTER TRIAL EVALUATING CONVENTIONAL AND DOUBLE DOSE OSELTAMIVIR IN THE TREATMENT OF IMMUNOCOMPROMISED PATIENTS WITH INFLUENZA

PROTOCOL NUMBER: NV20234

VERSION NUMBER: F

EUDRACT NUMBER: 2006-002468-24

IND NUMBER: 53,093

TEST PRODUCT: oseltamivir (Tamiflu® RO 64-0796)

PHASE: IIIb

INDICATION: Treatment of influenza in immunocompromised patients

SPONSOR: F. Hoffmann-La Roche Ltd

Objectives

Primary

To evaluate prospectively the safety and tolerability of oseltamivir for the treatment of influenza in IC patients under standard and double dose, and characterize the effects of oseltamivir in IC patients on the development of resistant influenza virus (see 4.6).

Secondary

To evaluate the effects of conventional and double dose oseltamivir in IC patients on:

- The population pharmacokinetics of *both oseltamivir and oseltamivir carboxylate* in IC patients with confirmed influenza infection, through the application of established population pharmacokinetic (PK) models to the sparse plasma concentration data generated.
- The virologic course of influenza (proportion shedding and viral loads at different timepoints)
- The time to resolution of influenza symptoms
- The clinical course of influenza (fever, symptoms, secondary illnesses as evidenced by otitis media, bronchitis, pneumonia, or sinusitis)
- To explore the relationship of metrics of exposure (e.g., AUC, C_{min}) to relevant pharmacodynamic endpoints

Study Design

Description of Study

This is a double-blind, randomized, multi-center trial of twice daily, conventional and double dose oseltamivir for the treatment of influenza in IC patients. Patients will be stratified by age (<13 vs. >12 years), transplant status (yes vs. no), time since onset of flu symptoms and treatment start (up to 96 hours) (≤ 48 vs. >48 hours) and vaccination status (yes vs. no).

Number of Patients

A minimum of 166 (83 per arm) to allow an adequate number of influenza A patients per arm; including 50 transplant recipients *and at least 15 paediatric patients*.

Number of Centers

Approximately 125 centers in the Northern and Southern Hemispheres

Target Population

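### Ages 13-17 are grouped in conflicting ways for efficacy and virology, and the individual-symptom table for children, taken as labelled, mixes two diaries

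*SAP*

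**What the plan says.** Section 4.4 has all efficacy summaries "carried out separately for adults (patients ≥ 18 years) and paediatrics (patients <13 years old", and adds: "Adolescent data (patients aged between ≥ 13 and <18 years old) will be listed as appropriate". Appendix 4 repeats, more firmly, that adolescents are only listed for efficacy.

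Section 4.8 presents the incidence of viral shedding "by visit (adults and adolescents mITTi", with a separate output for paediatrics.

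The Appendix 5 legend reads "CH = children (1 ≤ age < 18), PED = paediatric (1 ≤ age <13". The N.B. below it places TTR of symptoms and temperature in three sets: ≥18, ≥13 (adults plus adolescents) and <13. It continues: "for all other efficacy, virology and safety data adults will be separated from children (<18". In Table A5.1 the individual-symptom row is labelled Adults and Children, with outputs "t_ef_ttais_MITI_AD t_ef_ttais_MITI_CH".

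On instruments, Appendix 3 opens: "The purpose of the patient diary is for all adults (13 years and older". That diary has 7 symptoms scored 0-3. The children's diary has 18 items and adds a code 4 for not known or not applicable. Section 2.2.2.1 likewise ties seven symptoms to adolescents and adults, and 18 items to children.

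**The concern.** A programmer cannot follow all of these sections at once. Depending on which one is used, the same 15-year-old counts as an adult, counts as a child, or appears only in a listing. Tables for what looks like one age group could then cover different patients from endpoint to endpoint. The choice could also be settled informally at the table-shell stage, or after data have been seen.

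The individual-symptom row raises a second problem. A table for everyone under 18 would draw on two instruments with different item sets and response codes, and the SAP gives no mapping between them.

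**Working it through.** No sample size, power or event figure is involved, so the check is a side-by-side reading of where each source places ages 13-17.

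| Endpoint | 4.4 and Appendix 4 | 4.8 | Appendix 5 N.B. | Table A5.1 row |
|---|---|---|---|---|
| Shedding by visit | listed only | with adults | with children (<18) | Adults / Children, suffix CH (<18) |
| Viral-load change | listed only | adults; paediatrics (no ages given) | with children (<18) | Adults / Children, suffix CH (<18) |
| Peak viral titre | listed only | not covered | with children (<18) | Adults / Children, but suffix PE |
| TTR, all symptoms | listed only | not covered | with adults (≥13) | Adults; Adults + Adolescents; Paediatric |
| TTR, individual symptoms | listed only | not covered | with adults (≥13) | Adults / Children, suffix CH (<18) |
| TTR of fever, main row | listed only | not covered | with adults (≥13) | Adults; Adults + Adolescents; Paediatric |
| TTR of fever, benchmarking plot | listed only | not covered | with adults (≥13) | ≥18 versus <18 |

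Three things follow.

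1. The listing-only rule conflicts with every summary in Appendix 5 that includes adolescents. For shedding by visit, 4.8 and Table A5.1 also put them on opposite sides of the split.
2. Table A5.1 departs from its own N.B. in two rows: individual symptoms (CH, <18) and the fever benchmarking plot (split at 18), where the N.B. splits at 13.
3. The suffix PE is not in the legend, which defines only AD, ADOL, CH and PED. The fever outputs use PE for the group labelled Paediatric, while the peak-titre row uses it for a group labelled Children.

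Item count for the individual-symptom table, from the two diaries in Appendix 3:

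- Adult diary: 7 symptoms. Children's diary: 18 items.
- Same wording in both: headache, sore throat, cough = 3.
- Approximate counterparts: nasal congestion with nasal congestion or runny nose; aches and pains with muscle aches or pains; fatigue with low energy; feverish chills or sweats with fever = 4.
- Rows that could mix diaries: 3 + 4 = 7.
- Rows with no adult-diary counterpart: 18 − 7 = 11. These would hold only patients under 13.

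In a table for ages 1 to <18, the denominator and age mix would therefore change between the two kinds of row.

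**The case against.** The strongest reply is that no sentence says the diaries will be pooled. That reading rests on a row label and an output suffix, while the N.B. and section 4.4 both use <13 and section 2.2.2.1 defines all-symptom TTR by instrument. The row may simply be mislabelled. This stands, and the point is worded accordingly. It does not remove the need for correction. If the N.B. governs, the row and suffix are wrong. If the N.B. was meant to cover all-symptom TTR only, the row is as intended and the diaries do mix.

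A reader might infer that the children's individual-symptom results would be uninterpretable. The documents do not support that: the endpoint is analysed symptom by symptom, 11 rows would be unaffected by mixing, and both scales use the same ≤1 threshold. Nor do they show that children's diaries are mostly completed by proxies. The form lists possible raters without frequencies.

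A reader might also infer a shortfall against the synopsis figure of "at least 15 paediatric patients". That is an enrolment minimum, not an analysis-set size. The synopsis goes on to define paediatric and adolescent patients together as 1 to <18, so nothing is breached.

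It is likewise not established that 4.8 drops adolescents from viral-load change. It gives no ages for paediatrics, and the SAP uses the word unevenly: 2.2.6 splits resistance into adults and paediatrics, which 4.7 renders as ≥18 versus <18.

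Finally, different cuts for different endpoints can be deliberate. The safety split at 18 and the randomisation stratum at 12/13 are not in question.

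**Conclusion.** The contradiction holds. For efficacy and virology, ages 13-17 are listed only, grouped with adults, or grouped with children, depending on the section, and shedding by visit receives two incompatible groupings. Taken as labelled, the children's individual-symptom table would combine the two diaries in up to about 7 rows and hold only under-13s in 11. This rests on CH meaning 1 to <18, as the legend states, and on diary use following the age-13 cut in Appendix 3.

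The consequence is limited. The affected outputs are secondary and descriptive, and no hypothesis is tested. The SAP does not say how many adolescents are expected, so any count of patients moved between tables would be a guess and none is offered. It would also go too far to say that adolescents appear in no efficacy summary, because the ≥13 TTR tables in Appendix 5 include them.

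**What to change.** Set one age rule per endpoint and apply it in 4.4, 4.8, Appendix 4 and Appendix 5:

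- **Individual-symptom TTR:** split by diary. Replace the CH output with a <13 output and add a ≥13 output, with ≥18 shown separately, as for all-symptom TTR.
- **Fever benchmarking plot:** align its age groups with the N.B.
- **Shedding, viral load and peak titre:** use ≥18 versus <18, as the N.B. already does and as 4.7 does for resistance. Other cuts are defensible, but this one needs the fewest changes. Correct the 4.8 groupings, state the ages there, and replace the PE suffix with a defined one.
- **Adolescents in 4.4 and Appendix 4:** replace the listing-only statements with a reference to the rule per endpoint.

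The cost is SAP wording, table-shell labels and one additional individual-symptom output. The under-13 symptom tables will be smaller than tables for everyone under 18 would have been.
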